6.5.7. Collection of medical history, demographic and lifestyle characteristics

Obtain the family medical history, demographic and lifestyle characteristics of the subject as required by the eCRF, by interviewing parent(s)/LAR(s) and/or reviewing the medical records and record data collected in the subject's eCRF. This includes family history of respiratory disease, living environment and household composition, breastfeeding, passive smoking and day-care attendance.

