6.6.3. Analysis of tertiary objectives: potential risk factors for RSV disease

For this objective, the analysis will be based on PPS.

The incidence, overall and by country, of first events of RSV-LRTI, RSV severe LRTI, RSV non severe LRTI (WHO definition) will be analysed using a Cox regression.

The following risk factors will be considered in the model:

- General:
 - Country of birth
 - Gender (as recorded in demography of extension phase)
 - Time of birth relative to the transmission season (see section 6.1.4.5)
- Characteristics at birth:
 - Gestational age at birth (see details section 6.1.4.1)
 - Birth weight (see details section 6.1.4.2)
 - Apgar at 5 mins of age (see details section 6.1.4.3)
 - Caesarian section
- Family history:
 - First degree relative with family history of asthma (see details section 6.1.4.4)
- Living environment and household composition:
 - Highest education level of the mother (see details section 6.1.4.6)
 - Highest education level of the father (see details section 6.1.4.6)
 - Number of people living in the household at month 3 (see details section 6.1.4.7)
200150 (EPI-RSV-005 BOD)

- Statistical Analysis Plan Amendment 1 Final
- Number of other children (<18 years old) living in the household at month 3 (see detail section 6.1.4.8)
- Subject in regular close contact with toddlers at month 3
- The child live in a surrounding where people smoke daily at month 3
- Breast feeding *

* Time dependent covariate; status is yes of subject ever breastfed from DOB until the end of breastfeeding given in the surveillance visit. Last day of month will be imputed for any partial date of breastfeeding end date.

As described in the section 11.1.5, covariates with univariate p-value less than 0.1 will be included in the multivariable model. The number of covariates included in the model will depend on the number of events (at least 10 events per covariates).

Please note that the multivariable model will be performed only if the number of events is sufficient (at least 10 events per covariates). In addition, depending on the data, other models could be explored or the model could be simplified.

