6.9. Neutralizing antibodies over time and protection against RSV disease analysis

6.9.1. Analysis of secondary objective: Association between RSV disease and cord blood neutralizing antibodies

The analysis will be based on PPS and will be done considering the 2 age intervals:

- 0-2 months
- 0-5 months

The analysis will be realized only on the first episode (and not recurrent events) occurring during the considered age interval using a stepwise approach.

Step 1: Descriptive analysis:

Descriptive analyses (seropositivity rate with 95% CIs, geometric mean, median, min, max) of RSV neutralizing antibodies in the baseline cord blood samples will be presented by WHO RSV LRTI and WHO RSV severe LRTI case status; and with overlapping and non-overlapping disease severity.

In addition, descriptive analyses (seropositivity rate with 95% CIs, geometric mean, median, min, max) of RSV neutralizing antibodies in the baseline cord blood samples will be analysed according to the following endpoints:

- All RSV positive nasal swab samples (see details 6.1.2)
 - WHO RSV LRTI
 - WHO RSV LRTI (excluding WHO RSV severe LRTI)
 - WHO RSV severe LRTI
- Descriptive analyses (mean, median, min, max) of the total viral load of RSV according to the quartiles of neutralizing antibodies detected in the cord blood will be described.

Step 2: Cox models:

The impact of the level of RSV neutralizing antibodies in the baseline cord blood samples on the incidence of first event of WHO RSV-LRTI and WHO RSV-severe LRTI separately will be assessed through Cox models.

Univariate and multivariable Cox models will be presented. The following covariates may be considered in the multivariable model

- General:
 - Country of birth
 - Gender
 - Time of birth relative to the transmission season
- Characteristics at birth:
 - Gestational age at birth
 - Birth weight
 - Apgar at 5 mins of age
 - Caesarian section
- Family history:
 - First degree relative with family history of asthma

Statistical Analysis Plan Amendment 1 Final

- Living environment and household composition:
 - Highest education level of the mother
 - Highest education level of the father
 - Number of people living in the household at month 3
 - Number of other children (<18 years old) living in the household at month 3
 - Subject in regular close contact with toddlers at month 3
 - The child live in a surrounding where people smoke daily at month 3
 - Breast feeding *

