11. ANNEX 1 STANDARD DATA DERIVATION RULE AND STATISTICAL METHODS

11.1. Statistical Method References

11.1.1. Computation of incidence rates

For each endpoint, the incidence rate (IR, number of episodes/endpoints per 100 personyears) will be calculated by dividing the number of subjects reporting first episode over the follow-up period by the total person-year. A 95% CI will be computed using an exact method for a Poisson variable as described below.

The person-time at risk for an event of interest (e.g. RSV-LRTI) will be calculated as the time between the date of birth and the end of the at-risk period or the earliest of the followings:

200150 (EPI-RSV-005 BOD)

Statistical Analysis Plan Amendment 1 Final

- Date of first diagnosis of event of interest (e.g. first episode of RSV-LRTI);
- Date when child reaches 2 years;
- Date of last contact (lost-to follow-up, defined as no contact by the subject's parent(s)/LAR(s) over the period of 3 planned contacts and/or 2 months and after a final attempt has been made by mail. Once this has been reached, the subject is censored at the time of last contact);
- Date of death.

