12.6. Serology

12.6.1. Secondary serology analysis

12.6.1.1. (SO2) To evaluate the association between RSV-associated LRTI, RSVassociated severe LRTI and RSV neutralizing antibodies in the baseline cord blood samples collected from subjects, at birth.

Template 40 Seropositivity rate and geometric mean titres of [RSV-A – RSV-B] neutralising antibodies in the cord blood, Overall and by country (PPS)

		≥[8 – 6]			GMT					
				95% CI		95% CI				
Country	Ν	n	%	LL	UL	value	LL	UL	Min	Max
Overall										
Each Country										

GMT = geometric mean antibody titer calculated on PPS subjects

N = Total number of subjects with available results

n/% = number/percentage of subjects with titer equal to or above [8 - 6]

95% CI = 95% confidence interval; LL = lower limit, UL = upper limit

MIN/MAX = Minimum/Maximum

Template 41 Seropositivity rate and geometric mean titres of [RSV-A – RSV-B] neutralising antibodies by subjects classified according to nonoverlapping disease severity categories, in the first 3 months and 6 months of life, [Overall and by country] (PPS)

					[8 – 6]			GMT						
						95%	6 CI	95% CI						
Country	Age interval		Ν	n	%	LL	UL	value	LL	UL	Min	Max	Q1	Q3
	0-2 months	Non Case												
[Overall – by Country]		WHO RSV LRTI (excluding WHO RSV severe LRTI)												
		WHO RSV severe LRTI												
	0-5 months													

GMT = geometric mean antibody titer calculated on PPS subjects

N = Total number of subjects in the given category with available result (a subject is assigned to a single category based on the highest severity of the symptom experienced)

n/% = number/percentage of subjects with titer equal to or above [8 – 6]

95% CI = 95% confidence interval; LL = lower limit, UL = upper limit

MIN/MAX = Minimum/Maximum

Q1/Q3 = Quartile 1/Quartile 3

Note :

Non case is defined as subject not experiencing WHO RS V LRTI or WHO RSV severe LRTI in the given time interval An episode is confirmed as RSV positive using swab sample by qRT-PCR

200150 (EPI-RSV-005 BOD)

Statistical Analysis Plan Amendment 1 Final

Template 42 Seropositivity rate and geometric mean titres of [RSV-A – RSV-B] neutralising antibodies by subjects classified according to overlapping disease severity categories, in the first 3 months and 6 months of life, [Overall and by country] (PPS)

						[8 – 6]		GMT						
			9		95% CI			95% CI						
Country	Age interval		Ν	n	%	LL	UL	value	L	UL	Min	Max	Q1	Q3
	0-2 months	Non Case												

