[Overall – by Country]		WHO RSV LRTI												
		WHO RSV severe LRTI												
	0-5 months													

GMT = geometric mean antibody titer calculated on PPS subjects

N = Total number of subjects in the given catoegory with available results

n/% = number/percentage of subjects with titer equal to or above [8 – 6]

95% CI = 95% confidence interval; LL = lower limit, UL = upper limit

MIN/MAX = Minimum/Maximum

Q1/Q3 = Quartile 1/Quartile 3

Note :

Non case is defined as subject not experiencing WHO RS V LRTI or WHO RSV severe LRTI in the given time interval An episode is confirmed as RSV positive using swab sample by qRT-PCR

There may have been multiple swabs for an episode. In such cases, the swab with highest viral load was considered for this analysis

Template 43 [Univariate – Multivariate] estimated coefficients for Cox models with RSV-A and RSV-B by seropostivity status, for first WHO [RSV-LRTI – RSV Severe LRTI] episode, over the follow-up period from [0-2 months – 0-5 months] (PPS)

Characteristics	Category	Number of				
		Observations		Hazard		.
		Used in the	Event		n value	Global p-
	O	model	Event	(95% CI)	p-value	value
levels in cord blood	Seronegative					
	Seropositive					
RSV-B maternal antibodies levels in cord blood	Seronegative					
	Seropositive					
Country	Argentina					
	Missing					
Gender	Female					
	Male					
	Missing					
	Within transmission					
Time of birth	season					
	Outside transmission					
	season					

200150 (EPI-RSV-005 BOD)

	Statistical Analysis Plan Amendment 1 Fina											
Characteristics	Category	Number of Observations Used in the model	Event	Hazard ratio (95% CI)	p-value	Global p- value						
Gestational age at birth	<= 36 weeks											
	>36 weeks											
Birth weight	< 2.5 kg											
	>= 2.5 kg											
Apgar at 5 mins of age	0-3											
	4 – 6											
	>= 7											
	Missing											
First degree relative with FH of	Yes											
asthma	No											
	Missing											
Highest education level of the	Yes											
mother: Higher education /	No											
university	Missing											
Highest education level of the	Yes											
father: Higher education /	No											
university	Missing											
Number of people living in the	1-3											
household at Month 3	4-6											
	>=7											
Number of other children (<18	0											
years old) living in the	1-2											
household at Month 3	>=3											
Subject in regular close contact	Yes											

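### SAP 6.9.1 adjusts the 0-2 and 0-5 month Cox models for household, toddler-contact and smoking values taken at month 3, after all or much of the events have occurred

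*SAP*

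**What the plan says.** SAP 6.9.1 addresses a secondary objective, the association of cord-blood neutralizing antibody with RSV-LRTI. On the windows it states: "The analysis will be based on PPS and will be done considering the 2 age intervals", namely 0-2 and 0-5 months. The titles of Templates 41 and 42 show that these mean "in the first 3 months and 6 months of life". On events: "The analysis will be realized only on the first episode (and not recurrent events) occurring during the considered age interval". Under SAP 11.1.1, person-time "will be calculated as the time between the date of birth and the end of the at-risk period".

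Four candidate covariates for the multivariable model carry a month-3 label: "Number of people living in the household at month 3", the number of other children, regular toddler contact, and "The child live in a surrounding where people smoke daily at month 3". SAP Table 15 marks all four as not time-dependent; only breast feeding is. A covariate enters if its univariate p-value is below 0.1 and there are at least 10 events per covariate. SAP 6.6.3 uses the same four in the risk-factor model for first events over 2 years.

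Protocol 6.5.7 describes what is obtained at enrolment: "This includes family history of respiratory disease, living environment and household composition, breastfeeding, passive smoking and day-care attendance". Protocol Table 7 places this at Visit 2, within 5 working days of birth, and Protocol 6.5.13 treats the quarterly contact as an update of the Visit 2 data. The SAP gives no reason for choosing month 3, sets no landmark there, and does not list the choice in Section 9 among its departures from the protocol.

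**The concern.** A fixed covariate in a Cox model with origin at birth is treated as known from day 0. A month-3 value is not known then, and this opens two routes to bias.

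- **Selection.** Having a value requires still being followed at about month 3. An infant who withdraws, is lost or dies earlier has none. In the 0-2 month model such infants either drop out of the fit or form a Missing class made up largely of short follow-up. Missingness is then tied to censoring.
- **Reverse causation.** Parents may change smoking habits or the infant's contacts after an early respiratory illness. The changed value would then be used to explain the illness that prompted the change.

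The p<0.1 screen adds to this, because an association created in either way can itself bring the covariate into the model. At stake are the hazard ratios reported for these factors and, through adjustment, the hazard ratio for cord-blood antibody.

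**Working it through.** No sample-size or power figure depends on this point, so there is nothing of the plan's own to reproduce. The check compares event times with covariate times.

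**Inputs.** Event windows: 0 to <3 and 0 to <6 months (SAP 6.9.1; Templates 41-45). Origin: birth (SAP 11.1.1). Covariate time: month 3, fixed (SAP 6.9.1, Table 15). Alternative covariate time: Visit 2, within 5 working days of birth (Protocol Table 7). For the 2-year window: RSV-LRTI hospitalization rates per 1000 children-years from Protocol Table 12.

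**0-2 month window.** It closes at age 3 months, when the covariate is taken. Share of events before the measurement: essentially 100%.

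**0-5 month window.** Let r be the hazard in months 0 to <3 divided by that in months 3 to <6. The two halves are equally long, so, ignoring depletion of the risk set, the share before month 3 is r/(1+r).

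- r = 0.5: 0.5/1.5 = 33%
- r = 1: 1/2 = 50%
- r = 2: 2/3 = 67%

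The documents give no rate by month within this window, so r is an assumption.

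**2-year window (SAP 6.6.3).** With rates a (0-5 months), b (6-11 months) and c (12-23 months), and a taken as flat within 0-5 months (assumption), the share before month 3 is 0.25a / (0.5a + 0.5b + c). Three Table 12 sources report all three bands:

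| Source in Table 12 | a, b, c | Share before month 3 |
|---|---|---|
| USA | 16.9, 5.1, 2.7 | 4.225/13.70 = 31% |
| New York/Tennessee | 18.5, 7.4, 0.4 | 4.625/13.35 = 35% |
| Tennessee | 44.1, 15.0, 3.7 | 11.025/33.25 = 33% |

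These are hospitalization rates standing in for all RSV-LRTI, so they only illustrate the order of size.

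**With Visit 2 values.** No event after enrolment precedes the covariate.

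**Missing values.** Templates 17 and 43-45 have a Missing row for toddler contact and smoking but none for the two household counts, so the handling of infants without those counts is not stated. If the planned 20% drop-out were uniform over 24 months (assumption), loss before month 3 would be 20% × 3/24 = 2.5%.

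**The case against.** The strongest reply has five parts.

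1. The eCRF is not in the documents. Protocol 6.5.7 names domains, not items, so a count of people, a count of children and a daily-smoking item at birth are not shown to exist in usable form. Template 4, under a heading on demographics at birth, labels other children, toddler contact and smoking as Month 3. This stands. A reader might infer that the replacement data are certainly in hand, but the documents support only that these domains are collected at Visit 2.
2. Toddler contact is not named among the birth data, and the quarterly list in Protocol 6.5.13 names neither smoking nor toddler contact. This also stands, and the fix allows for it.
3. Household size and number of children may change little in three months and are unlikely to respond to an infant's illness. For these the reverse-causation argument is weak. What remains is missing values linked to early exit.
4. In 6.9.1 the covariates only may be considered, they must pass the screen, the antibody effect is also shown in univariate models that do not use them, and SAP Section 7 calls the analyses descriptive. This limits the consequences, but it does not make a value recorded after the event a sound fixed covariate. SAP 6.9.1 also says that covariates passing the screen will be included, and Templates 43-45 already carry all four rows.
5. Loss before month 3 is probably small, and a value from the first days of life is itself an imperfect measure of later smoke exposure. Both points are fair. The second is a modest cost of the fix.

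**Conclusion.** The point holds for SAP 6.9.1. Month-3 values are applied back to birth as fixed covariates, although essentially all 0-2 month events and about half of 0-5 month events precede them. The half assumes a constant hazard; the range is 33% to 67% for an early hazard half to twice the later one. Infants who leave or die before month 3 have no value. The hazard ratios of these covariates can be biased, and so can the adjusted antibody effect if they enter the model.

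Three stronger readings are not supported. One is that the antibody result is biased by a known or large amount: neither size nor direction can be derived, and the univariate antibody estimates are untouched. Another is that all four covariates are equally open to reverse causation: this is plausible for smoking and contacts, not for household counts. The third is that the 2-year model of 6.6.3 is compromised to the same degree: on the illustration above about 65% to 69% of its events follow month 3.

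No co-primary estimate depends on this. It is still worth changing, because the protocol's own plan of baseline data with quarterly updates points to the remedy.

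**What to change.** - **0-2 and 0-5 month models (6.9.1):** replace the month-3 household counts and smoking item with the Visit 2 household-composition and passive-smoking data, after confirming that the eCRF items give the categories in SAP 6.1.4.7 and 6.1.4.8 and a usable smoking indicator. If an item is not usable, say so in SAP Section 9.
- **Toddler contact:** leave it out of the 0-2 month model. In the 0-5 month model use it only from its measurement date on. Either restriction can be lifted if a birth value exists.
- **2-year model (6.6.3):** use the Visit 2 value as baseline and apply quarterly updates only from their date onward, where they are recorded. The SAP already treats breast feeding as time-dependent.
- **Missing household counts:** state how they are handled.

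The cost is SAP wording and reprogramming of Table 15 and Templates 17 and 43-45. If the eCRF items suffice, no new data are needed. The small downside is that birth values may reflect later exposure slightly less closely.

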6.1.3. RSV neutralising antibody

Geometric means for RSV neutralising antibodies will be derived according to the following table:

Table 7Derivation rule for GMT calculation of RSV neutralizing Antibody

Assay	Raw result	Derivation for GMT calculation
RSV-A neutralising Antibody	<8	4
	≥8	Exact value
RSV-B neutralising Antibody	<6	3
	≥6	Exact value

Seropositivity status for RSV neutralising antibodies in cord blood samples will be derived according to the following table:

Table 8Derivation rule for seropositivity status of RSV neutralizing Antibody
in cord blood samples

Assay	Raw result	Derivation for seropositivity status
RSV-A neutralising Antibody in cord blood	< 8	NEG
	≥8	POS
RSV-B neutralising Antibody in cord blood	< 6	NEG
	≥6	POS

Seropositivity status for RSV neutralising antibodies in blood samples will be derived according to the following table:

Table 9Derivation rule for prevalence of infection of RSV neutralizing
Antibody in blood samples

Assay	Raw result	Derivation for infection status
RSV-A neutralising Antibody in blood sample	< 2 fold of expected value*	Non infected
month 2, 4, 6, and 12	≥ 2 fold expected value	Infected
RSV-A neutralising Antibody in blood sample	< 8	Non infected
month 18 and 24	≥ 8	infected
RSV-B neutralising Antibody in blood sample month 2, 4, 6, and 12	< expected value	Non infected
	≥ expected value	Infected
RSV-B neutralising Antibody in blood sample month 18 and 24	< 6	Non infected
	≥ 6	infected

*Expected value is calculated using Natural decay model.

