Descriptive analyses (seropositivity rate with 95% CIs, geometric mean, median, min, max) of RSV neutralizing antibodies at 2, 4, 6, 12, 18 and 24 months will be presented.

Prevalence of infection will be determined at the time of the analysis based on the measured antibody titer *vs*. the expected antibody level at the time of sampling based on the individual baseline (cord blood) value and the average, modelled decay rate for subjects with blood sampling at time point 2, 4, 6, and 12 month. RSV infection is defined as titers 2-fold higher than expected value. For subjects with blood sampling during second year of life, a sample with positive result will count as prevalence of infection.

All exact 95% CI will be two-sided, based on the Clopper-Pearson based on a mathematical relationship (see Fleiss et al (2003), p. 25) between the F distribution and the cumulative binomial distribution.

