6.9.3. Analysis of tertiary objective: natural decay of maternal neutralizing antibodies

The analysis will be based on total sub-cohort subject with blood sampling at month 2, 4, 6, and 12 for this objective.

The decay of maternal antibody levels over time will be analysed graphically and by a linear regression of the log of maternal antibody levels. A true, natural decay curve will be explored by stochastically reducing the sample to uninfected subjects only. The following steps will be taken to identify, confirmed and suspected infected subjects to eliminate these from the sample;

STEP 1: Subjects with an RSV positive *nasal swab* during the study before time of sampling will be eliminated. Note that such subjects are removed from the analysis because they are infected by RSV; as a consequence their antibody levels are no longer maternal antibody levels.

STEP 2: Run the model and compute expected value based on the decay curve for each subjects

200150 (EPI-RSV-005 BOD)

Statistical Analysis Plan Amendment 1 Final

STEP 3: Subjects with an antibody titer at the sampling time that is more than 2-fold above the expected value based on their baseline (cord blood) value and the established decay curve will be considered to have been infected, eliminated and the decay curve refined.

STEP 4: Step 3 is repeated up to 5 times until the most accurate decay curve is established.

The natural decay of antibody will be determined using linear regression between the log of antibody level (Y) and time t (age in months) with subject as a random effect. Indeed, all subjects have RSV neutralizing antibodies measured at birth (cord blood). And, each subject of the Total sub-cohort will be randomly selected to be sampled for RSV neutralizing antibodies at one of the following time points: 2, 4, 6, and 12 months. For the natural decay model, subjects will have maximum 2 RSV neutralizing antibodies measures, one at birth and one either at 2 months or 4 or 6 or 12 months.

A table will describe the decay rate and half-life statistics of the natural decay model.

A descriptive table will describe the serology status (positive/negative) according to the natural decay analysis.

A sensitivity analysis of the decay curve will be explored in sub-sample consisting of the subjects born 'off-season' as these have the lowest likelihood of having been infected.

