12.6.2. Tertiary serology analysis

12.6.2.1. (TO7) To assess the natural decay of maternal antibody levels using a single follow-up blood sample collected from a randomly selected subcohort of subjects at 2, 4, 6, 12, 18 and 24 months.

Template 48 Seropositivity rate and geometric mean titres of [RSV-A – RSV-B] neutralising antibodies of cord blood sample by subjects randomized to a timepoint for sampling(PPS sub cohort)

			[8 -	- 6]			GMT				
					95%	6 CI		95% CI			
Antibody		Ν	n	%	LL	UL	value	LL	UL	Min	Max
Anti-[RSV-A – RSV-B]	Subjects sampled at										
Neutralizing Antibody in	month 2										
cord blood	Subjects sampled at month 4										
	Subjects sampled at month 6										
	Subjects sampled at month 12										
	Subjects sampled at month 18										
	Subjects sampled at month 24										
	Overall										

GMT = geometric mean antibody titer calculated on PPS sub-cohorts subjects

N = Number of subjects with available results at both baseline and sampling timepoint

95% CI = 95% confidence interval; LL = lower limit, UL = upper limit

n/% = number/percentage of subjects with titer equal to or above [8 – 6]

MIN/MAX = Minimum/Maximum

Template 49 Number and percentage of subjects with an [RSV-A – RSV-B] positive *nasal swab* during the study before time of blood sampling (PPS sub-cohort)

	Total								
Blood sampling timepoint (month)	Ν	Ν	%						
2									
4									
6									
12									
18									
24									

N = Number of subject by time point

n/% = number / percentage of episodes in a given category

200150 (EPI-RSV-005 BOD)

Statistical Analysis Plan Amendment 1 Final

Template 50 Summary of sequential models of the natural decay of maternal antibody levels (Total sub-cohort)

			95 CI	%		
Sequential models	N	Natural decay rate	L	U L	Half- life	
1: Model with all subjects except subjects with an RSV positive nasal swab during the study before time of sampling						
2						
Final: Most accurate model						

Note:

Natural decay rate is defined using a using linear regression between the log of antibody level and time in months with subject as a random effect.

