Each step/model is used to reduce the sample to uninfected subjects only. Subjects with an antibody titer at the sampling time that is more than 2-fold above the expected value based on their baseline (cord blood) value and the established decay curve will be considered to have been infected, eliminated and the decay curve refined. The expected value of antibody titer of each subject is computed using based on their baseline (cord blood) value and the established decay curve defined using the natural decay rate at the previous step.

The decay model is fitted only using subject with blood sample at 2, 4, 6, and 12 month

The sequential analysis is repeated up to 5 times until the most accurate decay curve is established

N = Number of subjects used in the model

LL, UL for percentage = Lower and Upper confidence limits

Template 51 Decay rate of [RSV-A – RSV-B] maternal antibody levels assuming a fixed rate of decay Neutralizing antibodies per months) (PPS subcohort)

q1-q4: quartile of [RSV-A - RSV-B] cord blood antibodies

200150 (EPI-RSV-005 BOD)

Statistical Analysis Plan Amendment 1 Final

Template 52 Prevalence of [RSV A – RSV B – RSV] infection, at 2, 4, 6, 12, 18 and 24 months in a randomly selected sub-cohort of subjects by assessing antibodies in serum [Overall – by country] (PPS subcohort)

					95% CI	
Country	Time point (Month)	Ν	n	Proportion (in %)	LL	UL
[Overall – by country]	2					
	4					
	6					
	12					
	18					
	24					

N = total number of subject at time of sampling

n = number of subjects with an antibody titer at the sampling time that is more than 2-fold above the expected value for month 2, 4, 6, and 12 month subject, and number of subject with antibodies in serum above [8 – 6] for month 18 and 24 subjects

LL, UL for percentage = Exact 95% Lower and Upper confidence limits

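### At months 2 to 12, RSV infection status rests on serum titre alone, so a child with an earlier RSV-positive swab can be tabulated as uninfected; a titre-or-swab figure should stand beside it.

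*SAP*

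**What the plan says.** A secondary objective is the prevalence of RSV infection at six ages in the seroprevalence sub-cohort, with one blood sample per child (protocol 2.1.2; SAP 3.2).

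- **SAP 6.9.2**, months 2 to 12: "RSV infection is defined as titers 2-fold higher than expected value". The expected value comes from the child's cord titre and the modelled decay; the Table 9 footnote says "Expected value is calculated using Natural decay model".
- **SAP Table 9** (6.1.3), months 2 to 12: the threshold for infection is "≥ 2 fold expected value" for RSV-A but "≥ expected value" for RSV-B.
- **SAP Template 52** (12.6.2.1) applies the 2-fold criterion at every first-year time point, with no separate rule for RSV-B; its footnote reads "n = number of subjects with an antibody titer at the sampling time that is more than 2-fold above the expected value for month".
- **SAP 6.9.3 Step 1**, on children with an RSV-positive swab before blood sampling: "Note that such subjects are removed from the analysis because they are infected by RSV".
- **SAP Template 49** counts those children by time point, for RSV-A and RSV-B, on the per-protocol sub-cohort that Template 52 also uses.
- **Protocol 4.1** defines RSV infection by RT-qPCR on a swab, whereas **protocol 9.7.2** analyses this objective through an antibody score.

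SAP section 9 (changes from planned analyses) adds no swab term to the prevalence definition.

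**The concern.** A young infant's neutralizing titre combines maternal antibody with the infant's own. If the two add, a titre at twice the expected maternal value requires the infant's own response to be at least as large as the maternal antibody that remains. That is a demanding test at months 2 to 6 and an easy one by month 12, so the rule's sensitivity rises with age. Part of any increase in reported prevalence from month 2 to month 12 could then come from the rule rather than from infection.

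The plan already holds independent evidence on some of the missed children. A PCR-confirmed infection before the draw is accepted as infection in 6.9.3 and ignored in 6.9.2. What is at stake is how far the age trend in Template 52 can be trusted, and whether confirmed infections appear as uninfected without comment.

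**Working it through.** **Plan's own figure.** The only number stated for this endpoint is the sub-cohort size: 200 + 200 + 250 + 300 + 450 + 600 = 2000, which matches protocol Table 1. The documents give no prevalence, no sensitivity of the titre rule and no residual variance.

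**Direction.** The children meeting titre rule OR prior positive swab include all those meeting the titre rule. Leaving out the swab can therefore only lower the numerator.

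**Step 1: expected swab-positive children before the draw.** Inputs from protocol 9.3: RSV LRTI hospitalization rates of 16.9 to 44.1 per 1000 child-years below 6 months, 5.1 to 15.0 at 6 to 11 months (Table 12), and a multiplier of 8 from hospitalized to all RSV LRTI. Share = 1 − exp(−8 × cumulative hospitalization rate). Month 2, low end: 1 − exp(−8 × 0.0169 × 2/12) = 2.2%.

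| Month | Allocated | Swab-positive share | Children |
|---|---|---|---|
| 2 | 200 | 2.2–5.7% | 4–11 |
| 4 | 200 | 4.4–11.1% | 9–22 |
| 6 | 250 | 6.5–16.2% | 16–40 |
| 12 | 300 | 8.4–21.1% | 25–63 |

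This assumes that every allocated child is sampled and that every RSV LRTI is swabbed.

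**Step 2: share of swab-positive children the titre rule misses.** This was simulated with the SAP's iterative decay fit. All titre inputs are assumptions: cord GMT 1000 (ln-SD 0.8); half-life 1.2 or 1.8 months; residual ln-SD 0.3, 0.5 or 0.7; infant response GMT 60 or 200 (ln-SD 0.8); infection hazard 0.07 per month; 30% of infections swab-positive, independent of titre; titres below 8 set to 4. Eight combinations were run. The hazard and the 30% imply swab-positive shares of about 3.9%, 7.3%, 10.3% and 17.0% at months 2, 4, 6 and 12, inside the ranges of Step 1.

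| Month | Swab-positives missed | Points added by titre-or-swab |
|---|---|---|
| 2 | 57–91% | 2.2–3.6 |
| 4 | 24–71% | 1.8–5.3 |
| 6 | 5–52% | 0.6–5.4 |
| 12 | at most 4% | 0–0.6 |

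Month 2 check: 3.9% × 0.57 = 2.2 points; 3.9% × 0.91 = 3.5 points.

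**Step 3: cruder cross-check.** Taking the Step 1 shares and assuming that 25% to 75% of swab-positive children lack a 2-fold titre gives an understatement of 0.6–4.3 points at month 2, 1.1–8.3 at month 4 and 1.6–12.1 at month 6. At month 12, the highest share with the highest simulated miss rate gives 21.1% × 0.037 = 0.8 points.

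**Step 4: error in the other direction.** An uninfected child exceeds twice the expected value with probability 1 − Φ(ln 2 / residual ln-SD): 1.0% at 0.3, 8.3% at 0.5 and 16.1% at 0.7. At month 2 with half-life 1.2 and response GMT 60, titre-only prevalence was 1.8% against a true 13.1% when the ln-SD was 0.3, and 19.6% against a true 13.0% when it was 0.7.

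**Step 5: the RSV-B row of Table 9.** With a threshold of 1 × expected and residuals symmetric on the log scale (assumption), about half of uninfected children would be called infected. The 2-fold factor in 6.9.2 and Template 52 does not produce that result, so the passages conflict.

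**The case against.** The strongest reply is that serology is the pre-specified estimand. The objective names serum antibodies, protocol 9.7.2 scores the titre, and the sub-cohort is a seroprevalence sub-cohort. A swab is taken only at an examination visit prompted by suspected LRTI. A titre-or-swab rule would therefore make prevalence depend on symptom severity and on how well surveillance worked in each country, which a randomly timed serum sample avoids. SAP section 9 itself reports children with an examination visit but no surveillance visit. This stands, and it is why the serology-only figure should not be replaced.

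It is also fair that Template 49 already shows the swab-positive counts. It does not show how many of those children Template 52 classes as uninfected, so the two tables cannot be linked by a reader.

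A reader might infer that the 2-fold rule biases prevalence low overall. The documents do not support that: without a residual variance, chance exceedances could outweigh the missed infections, as Step 4 shows. Nor do they support the view that the rule is blind to infection at months 2 to 6; in the simulation it still detected 9% to 43% of swab-positive children at month 2 (100% less the missed share).

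A reader might also carry the point over to months 18 and 24, where "For subjects with blood sampling during second year of life, a sample with positive result will count as prevalence of infection". There the threshold is only 8 (RSV-A) or 6 (RSV-B). With an assumed response GMT of 64 and SD of 1.5 log2 units, about 2.3% of infected children would fall below 8 and 1.1% below 6, so the gap is negligible.

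**Conclusion.** The concern holds in a limited form. For months 2 to 12, a child whom 6.9.3 treats as infected on PCR evidence can be reported as non-infected in Template 52. This omission works downward and is concentrated at months 2 to 6: about 2 to 4 percentage points at month 2, 2 to 5 at month 4, 1 to 5 at month 6 and under 1 at month 12. Those sizes rest on the assumed titre distributions, half-lives, infection hazard and swab detection share in Step 2. The cruder calculation in Step 3 reaches 12 points at month 6 if three quarters of swab-positive children are missed.

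The net bias of the titre rule is undetermined. The conflict over the RSV-B threshold is a separate defect in the text and needs no assumption to establish. The remedy is a cheap addition to the reporting; the pre-specified endpoint stays.

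**What to change.** 1. Keep the serology-only prevalence as the main figure in Template 52.
2. Add a second figure by time point: titre rule met, or RSV-positive RT-qPCR swab (SAP 6.1.2) dated before the blood sample.
3. Beside it, report the share of the swab-positive children in Template 49 that the titre rule detects at each time point, with an exact interval. With perhaps 4 to 11 such children at month 2, the interval will be wide.
4. State in 6.9.2 that swabs come only from examination visits for suspected LRTI, so the added infections depend on severity and on country surveillance.
5. Reconcile the RSV-B row of Table 9 with the 2-fold rule in 6.9.2 and Template 52.

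The cost is SAP wording and one cross-tabulation. Template 49 already requires swab results to be linked to blood-sampling dates on the same analysis set, separately for RSV-A and RSV-B. No new data are needed.
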